The sample size for this study is based on clinical rather than statistical considerations, taking into account the limited number of patients with hemophilia A without inhibitors available for participation in clinical studies and in an effort to collect sufficient data to assess the safety and efficacy of emicizumab.

The sample size calculation is based on the evaluation of the primary efficacy endpoint, defined as the number of bleeds over time (i.e., bleed rate) with emicizumab (treatment group, λ_t) versus no prophylaxis (control group, λ_c), which are said to follow a negative binomial (NB)

distribution. With consideration of enrollment feasibility, a sample size of 75 patients, assuming an allocation ratio of 2:2:1 (30 patients in each randomized treatment group and 15 patients in control group), will achieve a power of more than 90% assuming a mean ABR of 4 and 14 bleeds (with variances = mean \times 10) for the emicizumab treatment and control arms respectively, representing an expected 71% reduction in the ABR compared to the control arm. Initial sample size calculations were performed with East[®], Version 6 (Cytel, Cambridge, MA), assuming the patients from each treatment group are followed up to 0.5 units of time (i.e., 24 weeks).

However, the above approach to sample size calculation assumes similar follow-up for each patient. Because this is unlikely to be seen in the study, power was also estimated by simulation to account for different follow-up times among patients. Conducting simulations on the basis of an NB regression model including an offset variable to account for variable follow-up times, with all other assumptions remaining the same as previously described, the sample size is projected to have greater than 90% power at the 2-sided 0.05 level of significance.

The analysis will include all enrolled patients regardless of their length of follow-up. Therefore, to ensure the analysis is based on sufficient follow-up data and with 2:2:1 treatment to control randomization, approximately 34 patients in each randomized emicizumab treatment arm (68 in total) and 17 patients in the control arm (approximately 85 patients in total) will be enrolled.

With a minimum of 40 and a maximum of 60 patients enrolled in the open-label prophylactic emicizumab arm, and assuming a mean ABR of 4 and variance of 4×10 , this number is considered sufficiently powered to evaluate the efficacy endpoint in this cohort; the treatment will be considered to provide adequate control if the upper limit of the one-sided 97.5% CI around the mean ABR is less than or equal to 6.

The primary safety consideration in determining the sample size was the ability to sufficiently evaluate the safety profile of emicizumab as assessed by adverse events. Under the assumption that the occurrence of an adverse event can be adequately modeled using the binomial distribution, the planned sample size of 108–128 patients in the emicizumab treatment groups allows observation of adverse events having a true incidence rate of 1% with a probability of 0.66–0.72.

During the study, a re-assessment of the initially specified sample size based on aggregated (not by treatment arm) data to-date (and potentially from the non-interventional study [BH29768] findings) may be performed. This may result in an increase in sample size, if necessary, to maintain adequate power without affecting the type 1 error rate. Study integrity will be upheld, as access to information via aggregated analyses and their results will be minimized to limit operational bias.

Regarding the effect of emicizumab on changes of DSC from baseline at Weeks 23–24 or 47–48 in patients with hemophilia A, there is currently no published information on the variability or clinical significance of longitudinal changes in this measure with the study device in patients with hemophilia A. No data are available to allow detailed sample size calculation of these exploratory objectives. Participation will be offered to all patients in the study, leading to a maximum sample size of 145 patients. Of note, 40 subjects (20 per treatment group) were deemed sufficient to evaluate the related objectives with an adequate level of precision in similar studies that enrolled patients with chronic obstructive pulmonary disease, such as WB29804 Activity Substudy.

Interim Analyses

No interim analysis for efficacy is planned.

LIST OF ABBREVIATIONS AND DEFINITIONS OF TERMS

Abbreviation	Definition
2wks	every 2 weeks
ABR	annualized bleeding rate
ADA	anti-drug antibody
aHUS	atypical hemolytic uremic syndrome
aPCC	activated prothrombin complex concentrate
AUC	area under the curve
BA	bioavailability
BMI	body mass index
C _{max}	maximum plasma concentration
cts	counts
CVAD	central venous access device
DSC	daily steps count
EC	Ethics Committee
eCRF	electronic Case Report Form
EDC	electronic data capture
ePRO	electronic patient-reported outcome
EQ-5D-5L	European Quality of Life-5 Dimensions-5 Levels
FDA	U.S. Food and Drug Administration
FEIBA	Factor Eight Inhibitor Bypassing Activity
FIX	factor IX
FIXa	activated factor IX
FVIII	factor VIII
FX	factor X
FXIII	factor XIII
HCP	healthcare provider
HIPAA	Health Insurance Portability and Accountability Act
HJHS	Hemophilia Joint Health Score
HRQoL	health-related quality of life
iDCC	independent Data Coordinating Center
iDMC	independent Data Monitoring Committee
ICH	International Council for Harmonisation
IFU	Instructions for Use
IgG4	immunoglobulin G4
IMP	investigational medicinal product
IND	Investigational New Drug (application)
IRB	Institutional Review Board

Abbreviation	Definition
ITI	immune tolerance induction
IV	intravenous
IxRS	interactive voice or Web Response System
LPLV	last patient, last visit
MAD	multiple ascending dose
NB	negative binomial
NOAEL	no observed adverse effect level
PAQ	physical activity questionnaire
PD	pharmacodynamics
PK	pharmacokinetic
PRO	patient-reported outcome
QTcF	QT interval corrected using Fridericia's formula
QoL	quality of life
RCR	Roche Clinical Repository
rFVIII	recombinant FVIII
rFVIIa	recombinant activated factor VII
SAD	single ascending dose
SAP	Statistical Analysis Plan
SC	subcutaneous
SQ-ISHI	Satisfaction Questionnaire–Intravenous Subcutaneous Hemophilia Injection
$t_{1/2}$	half-life
TMA	thrombotic microangiopathy
t_{max}	time to maximum plasma concentration
ULN	upper limit of normal
VAS	visual analog scale
WHO	World Health Organization
wk	week

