 - Spontaneous bleeds over time (spontaneous bleed rate)
 - Joint bleeds over time
 - Target joint bleeds over time (target joints are defined as joints with ≥ 3 bleeds occurring in the same joint over the last 24 weeks prior to study entry)

HRQoL of patients according to Haem-A-QoL (aged ≥ 18) or Haemo-QoL-Short Form (aged 12–17) scores after 24 weeks

Health status of patients according to EuroQoL Five-Dimension-Five Levels Questionnaire (EQ-5D-5L) scores after 24 weeks

- To evaluate the efficacy of prophylactic emicizumab administered at 1.5 mg/kg/wk subcutaneously for patients previously treated with prophylactic FVIII on the basis of the following endpoint:

Maintaining adequate control of bleeding by evaluation of the bleed rate *

* Analyses will be performed for treated bleeds and all bleeds.

Exploratory Objectives

The exploratory objectives for this study are as follows:

- To assess satisfaction regarding treatment with emicizumab prophylaxis versus FVIII prophylaxis according to the Satisfaction Questionnaire–Intravenous Subcutaneous Hemophilia Injection (SQ-ISHI) in patients previously treated with prophylactic FVIII
- To assess treatment preference for emicizumab prophylaxis versus FVIII prophylaxis or episodic therapy according to the preference survey
- To assess changes in number of days away from school/work during treatment with prophylactic emicizumab compared with no prophylaxis
- To assess changes in number of hospitalization days during treatment with prophylactic emicizumab compared with no prophylaxis
- To assess potential pharmacodynamic (PD) biomarkers of emicizumab, including but not limited to aPTT, thrombin generation, and FVIII activity
- To assess potential serum and plasma biomarkers of bone and joint health
- To evaluate the effect of emicizumab prophylaxis treatment on activity compared with activity at baseline.
- To evaluate the effect of emicizumab prophylaxis treatment on activity compared with no prophylaxis

Safety Objective

The safety objective for this study is to evaluate the overall safety of prophylactic emicizumab compared with no prophylaxis in patients with hemophilia A without inhibitors on the basis of the following endpoints:

- Incidence and severity of adverse events
- Incidence and severity of thromboembolic events
- Changes in physical examination findings and vital signs
- Incidence of laboratory abnormalities
- Incidence and severity of injection-site reactions

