Summary statistics of the number of work/school days missed and days hospitalized will be presented by treatment arm. Summary statistics will also be presented for the SQ-ISHI and emicizumab Preference Survey. PD parameters (e.g., aPTT, parameters derived from thrombin generation, FVIII activity) and markers related to bone and joint health will be presented using summary statistics, including arithmetic and geometric means, median, range, standard deviations, and coefficients of variation.

For the activity assessment all enrolled subjects that contribute reliable activity data (i.e., at least 8 valid days) will be analyzed. There will be no imputation of missing data. Subjects will be grouped according to the treatment regimen to which they are assigned in the main study. Because of the exploratory nature of the study, there will be no type-1 error control for multiplicity. Enrollment, discontinuations, protocol violations/deviations, and duration of activity monitoring follow-up will be summarized. Demographic and baseline characteristics, such as age, sex, race/ethnicity, and weight will be summarized using descriptive statistics. Relative change is defined as $100 \times (DSC_{\text{Week } n} - DSC_{\text{baseline}}) / DSC_{\text{baseline}}$.

Relative change from baseline at Week 25 or 49 in mean DSC and activity counts (total, mean, and peak) will be calculated within each treatment group provided the patient has reported data on at least 8 days within the 14 day observation period. Subject-level averages at each timepoint will be presented via dot-plots and descriptive statistics by treatment group.

The main comparisons will be within-patient changes, calculated within each treatment group. Within the control arm, where patients are expected to switch to emicizumab prophylaxis treatment at 24 weeks, an additional comparison of the relative change from Week 25 to Week 49 will be performed.

Formal statistical modeling may be performed as appropriate. Such analysis will be based on between-treatment comparisons of the change in activity from baseline to Week 25 between patients receiving emicizumab prophylaxis (Arms A or B) versus no prophylaxis (Arm C).

Determination of Sample Size

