The reason for the use of FVIII products will be documented (e.g., bleeding, one time prophylaxis, etc.). A thorough documentation of the treatments for bleeds will be required, including agent, start time, dose, route of administration, and number of infusions needed to treat the bleed.

A non-interventional study (BH29768) has been initiated to document the number and types of bleeds and current treatment with episodic or prophylactic FVIII agents, as well as to collect information on HRQoL, health status, and safety in patients with hemophilia A. The assessments in the non-interventional study will mitigate the risk of underreporting of bleeds that likely occurs in the real world, and the resulting data will serve as a source of comparator information for some analyses conducted in the Phase III clinical studies, including this study. In addition, the non-interventional study will enable earlier identification and confirmation of patients who may qualify for the Phase III clinical study. It is anticipated that a significant number of patients participating in Study BH29768 will enroll in this study, as long as they meet the inclusion and exclusion criteria and are able to enroll at a participating site while the study is open for enrollment.

Activity assessment will be conducted at all sites participating in this study, and all patients screened and enrolled will be expected to participate. Participation will not be mandatory and will not impact participation in Study BH30071. Patients will be asked to wear the study device for 2 weeks during Weeks 1–2, 23–24, and 47–48. Patients will return their study devices to the respective site at Weeks 3, 25, and 49 and each site will transfer the data from the device to the database. These data will be analyzed to generate the daily step count (DSC) values for each patient.

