Participants will be instructed to wear the device for 2 weeks at the beginning of the study and for 2 weeks approximately every 6 months subsequently. Intermittent sampling of approximately a week was commonly employed in similar studies that assessed physical activity in patients with chronic diseases (Lavie et al. 1992; Watz et al. 2014; Ahn et al. 2015; Chu et al 2015; Yu et al. 2015). The incremental added value of additional days of data collection (Briscoe et al. 2014) is likely offset by diminishing compliance with a longer observation period. Due to logistical considerations, baseline activity will be captured during the first 2 weeks after enrollment rather than prior to starting treatment. Although patients will have started emicizumab, its level will be below steady state, and the relatively short duration on emicizumab at this time is unlikely to inspire a change in activity habits. Therefore, activity during Weeks 1 and 2 is expected to be similar to pre-study activity, and a change, if any, from pre-enrollment will likely only underestimate the effect of emicizumab rather than overestimate it. The alternative approach of delaying initiation of therapy to allow measurement of baseline DSC may be unacceptable to many patients and investigators.

The purpose of this activity assessment in this study is to evaluate the effects of emicizumab treatment on patients' DSC as measured by a waist-worn ActiGraph (a medical device used to continuously monitor and measure activity through a triaxial accelerometer) in patients with hemophilia A. The data collected by the study device will be scored to identify active and rest periods for each patient within each 24-hour period. This device continuously captures frequency, duration, and intensity of acceleration and through a proprietary algorithm converts the pattern of motion into step counts and activity counts (a value used to quantify both intensity and duration of physical activity). Although steps are not counted directly, the number of steps for each individual can be reliably derived from data obtained by a waist-worn device (Gironda et al. 2007; Garriguet et al. 2015). In general, the available technology is well suited to accurately capture DSC (Case et al. 2015), supporting its use in this study.

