6.8 EXPLORATORY ANALYSES

Summary statistics of the number of work/school days missed and days hospitalized will be presented by treatment arm. Summary statistics will also be presented for the SQ-ISHI and emicizumab Preference Survey. PD parameters (e.g., aPTT, parameters derived from thrombin generation, FVIII activity) and markers related to bone and joint health will be presented using summary statistics, including arithmetic and geometric means, median, range, standard deviations, and coefficients of variation.

For the activity assessment all enrolled subjects that contribute reliable activity data (i.e., at least 8 valid days) will be analyzed. There will be no imputation of missing data. Subjects will be grouped according to the treatment regimen to which they are assigned in the main study. Because of the exploratory nature of the study, there will be no type-1 error control for multiplicity. Enrollment, discontinuations, protocol violations/deviations, and duration of activity monitoring follow-up will be summarized. Demographic and baseline characteristics, such as age, sex, race/ethnicity, and weight will be summarized using descriptive statistics. Relative change is defined as

$$100 \times (DSC_{\text{Week } n} - DSC_{\text{baseline}}) / DSC_{\text{baseline}}$$

Relative change from baseline at Week 25 or 49 in mean DSC and activity counts (total, mean, and peak) will be calculated within each treatment group provided the patient has reported data on at least 8 days within the 14 day observation period. Subject-level averages at each timepoint will be presented via dot-plots and descriptive statistics by treatment group.

The main comparisons will be within-patient changes, calculated within each treatment group. Within the control arm, where patients are expected to switch to emicizumab prophylaxis treatment at 24 weeks, an additional comparison of the relative change from Week 25 to Week 49 will be performed.

Formal statistical modeling may be performed as appropriate. Such analysis will be based on between-treatment comparisons of the change in activity from baseline to Week 25 between patients receiving emicizumab prophylaxis (Arms A or B) versus no prophylaxis (Arm C).

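### The randomised comparison of activity against no prophylaxis is only optional, while an uncontrolled within-arm change is the main activity comparison

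*Protocol*

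**What the plan says.** The exploratory objectives (Protocol 2.1.3 and synopsis) contain two on activity. The first compares activity on emicizumab with activity at baseline. The second is "To evaluate the effect of emicizumab prophylaxis treatment on activity compared with no prophylaxis".

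On timing, Protocol 3.1 says "Patients will be asked to wear the study device for 2 weeks during Weeks 1–2, 23–24, and 47–48". Appendix 1 schedules the measure for Arm C at Week 1 and again at Week 25, the visit at which Arm C starts emicizumab. Section 3.3.7 explains that "baseline activity will be captured during the first 2 weeks after enrollment rather than prior to starting treatment".

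On analysis, Protocol 6.8 says "The main comparisons will be within-patient changes, calculated within each treatment group". For Arm C, across its switch, "an additional comparison of the relative change from Week 25 to Week 49 will be performed". The between-arm analysis follows: "Formal statistical modeling may be performed as appropriate". Its contrast is then defined as change from baseline to Week 25, Arms A or B against Arm C. Section 6.8 also promises dot-plots and descriptive statistics by treatment group, with no control of type I error because the work is exploratory.

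**The concern.** Two objectives are listed, and the main comparison serves only the first. The second asks a between-arm question. The design can answer it with randomised, concurrently measured groups, but that answer depends on a discretionary model. Whether to fit it could be decided after the data have been seen.

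The within-arm change is a weak substitute. Randomised patients must have had at least 5 bleeds in the previous 24 weeks (Protocol 4.1.1), so some return toward usual bleeding, and with it usual activity, is plausible in every arm. Wearing a device and entering a study may also change behaviour at first. Season may add to this if enrolment is uneven over the year. A rise in Arms A and B could then be read as a drug effect even if Arm C rose as much.

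The protocol accepts this principle for bleeds. Section 3.3 argues that, for patients not previously on prophylaxis, a prospective randomised comparison is better than a historical control.

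**Working it through.** **No figure of the plan's own to reproduce.** Protocol 6.1 gives no effect size, SD or power for activity and says that no data allow a detailed calculation. Arm sizes come from 6.1: 85 patients at 2:2:1 gives 34, 34 and 17. Participation is optional (3.1), so these are maxima. SDs and seasonal amplitudes below are assumptions.

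**What each quantity estimates.** Let d be the drug effect on the change from Weeks 1–2 to Weeks 23–24, and s the time effect shared by all arms.

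- Change within Arm A or B: d + s
- Change within Arm C: s
- A minus C, or B minus C: (d + s) − s = d

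The within-arm change equals the drug effect only if s = 0. Arm C's Week 25 to Week 49 change has the same form, d + s over a later interval, so it does not fill the gap.

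**Spacing of the windows.**

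- Weeks 1–2 to 23–24: 22 weeks = 154 days; 154/365.25 × 360 = 152 degrees of the yearly cycle. The largest possible swing is 2 × sin(76°) = 1.94 × the seasonal amplitude.
- Weeks 1–2 to 47–48: 46 weeks = 322 days = 317 degrees, only 43 degrees from the same season.
- Weeks 23–24 to 47–48: 24 weeks = 168 days = 166 degrees.

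So each patient's baseline-to-Week-25 comparison is close to opposite in season. The Week 49 comparison with baseline is not.

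**Seasonal shift in a group mean with no drug effect.** Cosine cycle, relative change averaged over the enrolment window, range over start dates, one hemisphere:

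| Assumed amplitude | 6-month enrolment | Even 12-month enrolment |
|---|---|---|
| 5% | −5.9 to +6.4 points | +0.2 |
| 10% | −11.5 to +13.4 | +0.9 |
| 20% | −21.5 to +29.2 | +3.9 |

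With half the patients in the other hemisphere and 10% amplitude, the shift is 0 to about +2 points for any window.

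**If a within-arm 95% interval were read as a test** (n = 34, SD 30, SE = 30/√34 = 5.14): with no drug effect it would exclude zero in 6.7% of trials for a 2-point shift, 16% for 5 points and 49% for 10 points.

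**Precision of the randomised contrast.** SE = SD × √(1/n₁ + 1/n₂). The bracket is 1/34 + 1/17 = 0.088 for one arm against C, 1/68 + 1/17 = 0.074 pooled, and 1/20 + 1/20 = 0.100 for 20 per group. Half-width = 1.96 × SE; difference detectable with 80% power = 2.80 × SE. All in percentage points of relative change:

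| Assumed SD | Within-arm half-width, n = 34 | 34 v 17 half-width | 34 v 17 detectable | 68 v 17 detectable | 20 v 20 detectable |
|---|---|---|---|---|---|
| 20 | 6.7 | 11.6 | 16.6 | 15.2 | 17.7 |
| 30 | 10.1 | 17.5 | 25.0 | 22.8 | 26.6 |
| 50 | 16.8 | 29.1 | 41.6 | 38.0 | 44.3 |

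**The case against.** The best case for the plan has four parts.

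1. The within-patient change matches the versus-baseline objective, which is listed first. It is also the only option for Arm D (40–60 of 125–145 patients), which has no concurrent control. This stands, and is why within-arm results should be kept.
2. Arm C's change will be shown beside those of A and B, so an equal rise would be visible. This stands as an informal check, but no between-arm estimate or interval is promised.
3. The randomised contrast is already defined. This stands too. What is missing is the commitment to perform it.
4. The assessment is optional and exploratory. That limits the importance of the point but does not answer it.

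Three stronger readings are tempting and are not supported.

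- *Season will appear as a drug effect.* Section 3.3.4 expects enrolment from several continents over about a year, and 3.1 names the Americas, Europe, Africa and Asia-Pacific. On even enrolment the shift nearly vanishes. The rejection rates above also describe a test that the plan does not specify.
- *No committed analysis exists anywhere.* SAP 2.2.3, 4.2.8 and parts of 2.3.3 and 4.5.3 are blacked out, and the SAP's synopsis has a redaction where the protocol mentions activity level. The statement can be made only for the visible protocol text.
- *The sample-size note is wrong because Arm C cannot reach 20.* The note says "40 subjects (20 per treatment group) were deemed sufficient to evaluate the related objectives with an adequate level of precision" in COPD studies, as a remark and not as a requirement here. At full participation 34 versus 17 (0.088) is already more precise than 20 versus 20 (0.100).

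**Conclusion.** The point holds for the protocol as visible: the objective of comparing activity with no prophylaxis has no committed analysis, although the randomised data for it will be collected. This follows from the text and needs no assumption. That a within-arm change mixes drug and shared time effects follows from the design. How large those effects are cannot be determined from the documents, and the seasonal part matters only if enrolment is seasonally uneven.

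The randomised contrast is not a complete cure. It removes time effects common to the arms, but not open-label effects on motivation. Nor does it remove the unequal early schedule: Arms A and B attend at Weeks 1, 2 and 3, while Arm C attends at Week 1 and then Week 5. Weeks 1–2 also fall after randomisation and on treatment in A and B. Section 3.3.7 argues that this could only understate the effect.

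This is a worthwhile, inexpensive improvement to an exploratory analysis. It has no bearing on the primary endpoint.

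**What to change.** In Protocol 6.8 and the synopsis:

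- Replace *may be performed* with *will be performed* for the between-arm analysis.
- Name A versus C and B versus C (optionally also A and B pooled versus C) in daily step count at Weeks 23–24, adjusted for Weeks 1–2 steps and the bleed stratum (<9 or ≥9), as the main analysis for the versus-no-prophylaxis objective, with estimates and 95% intervals.
- Add a sensitivity analysis without the Weeks 1–2 adjustment, because that value is post-randomisation and on treatment in A and B.
- Keep within-arm changes, including Arm C's Week 25 to Week 49 change, as descriptive results for the versus-baseline objective and for Arm D.

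If the redacted SAP text already commits to such an analysis, align the protocol with it.

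No new data, visits or patients are needed. The cost is a wider interval, because Arm C has about 17 patients at most: about 1.7 times the within-arm half-width (17.5/10.1) at full participation, and wider still if participation is lower.
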